2.5.2 Secondary endpoints

- Measure weight stability at baseline and day 1 of every cycle for 6 months
- Food intake will be assessed by study staff at C1D1, C3D1, and end-ofstudy. A validated 24-hour recall questionnaire will be analyzed using the automated self-administered 24-hour Dietary Assessment tool (ASA-24)
- Assess stool frequency at C1D1 and C3D1 using a stool survey
- Stool consistency at C1D1 and C3D1
- Measurement fat-soluble vitamins (including Vitamins A, D, E, and K) at baseline and end-of-study
- Evaluate microbiome at C1D1 and C3D1
- Activity (steps taken, stairs climbed, sleep duration and disturbances, heart rate and intensity) will be collected using the wearable activity monitor (e.g., Fitbit Charge HR) daily for the duration of the study.

2.5.3 Exploratory endpoints

- Quality of life and symptoms of pain will be measured using the PROMIS-29 at baseline and day 1 of every cycle for 6 months
- Patient-reported response the therapy will be measured using FAACT at baseline and day 1 of every cycle for 6 months

- Measure fecal elastase at baseline
- Survival will be evaluated at every visit and every 6 months during 36month follow-up
- Safety and tolerability will be assessed by collecting adverse events throughout the study
- Research blood will be assessed for inflammatory biomarkers including: IL-6, interferon 1-alpha, TNF-alpha, Interleukin-1β, neuropeptide y, ZAG, ghrelin, CCK, GLP-1, PYY, glucagon and insulin at baseline and day 1 of every other cycle for 6 months and at the end-of-study visit. We will use standardized ranges for normal levels of the following assays.
- Presence of frailty phenotype using Fried's definition [50] will be evaluated
 at baseline and day 1 of every other cycle for 6 months by measuring
 patient grip strength, using a dynamometer during physical exam, a 15
 foot walk test, question about energy levels and activity (APPENDIX E)
- Assess body composition using computed tomography collected as standard of care every 8 weeks

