2.3 Patient-Reported Outcomes / Exploratory Objectives

- **2.3.1** To assess quality of life including pain assessment using PROMIS-29 at baseline and day 1 of every cycle for 6 months
- 2.3.2 To assess patient-reported response to therapy using FAACT (Functional Assessment of Anorexia/Cachexia Therapy) baseline and day 1 of every cycle for 6 months
- 2.3.3 Measure fecal elastase at baseline
- 2.3.4 Assess overall survival
- 2.3.5 Assess adverse events for safety and tolerability
- 2.3.6 Assess inflammatory biomarkers in research blood
- **2.3.7** Assess the presence of frailty phenotype
- **2.3.8** Assess body composition using computed tomography collected as standard of care every 8 weeks

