2.4.3 Exploratory Hypotheses

- Improve quality of life and symptoms of pain from baseline
- Patient-reported response the therapy will improve

- Fecal elastase may correlate with response to pancreatic enzyme supplementation
- Survival and response rate may benefit from a comprehensive approach to nutritional support
- Pancreatic enzyme supplementation will be safe and tolerable
- Weight loss and cachexia may be associated with genomic and stromal alterations in the tumor.
- · Inflammatory biomarkers may be improved
- The frailty phenotype may be improved
- Lean body mass may be maintained throughout treatment course

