5.1.16 Hand grip and 15 ft walk test

Hand grip using the hand-held dynanometer. Three assessments for each hand will be completed and recorded. A timed walk-test from first foot fall to last foot fall over 15 feet will be performed twice per assessment.

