APPENDIX E: Measures of Frailty phenotype

Table 1. Operationalizing a Phenotype of Frailty

A. Characteristics of Frailty	B. Cardiovascular Health Study Measure*
Shrinking: Weight loss (unintentional) Sarcopenia (loss of muscle mass)	Baseline: >10 lbs lost unintentionally in prior year
Weakness	Grip strength: lowest 20% (by gender, body mass index)
Poor endurance; Exhaustion	"Exhaustion" (self-report)
Slowness	Walking time/15 feet: slowest 20% (by gender, height)
Low activity	Kcals/week: lowest 20% males: <383 Kcals/week females: <270 Kcals/week
	C. Presence of Frailty
	Positive for frailty phenotype: ≥3 criteria present
	Intermediate or prefrail: 1 or 2 criteria present

Table from Fried et al. 2001

Protocol for frailty criteria*:

- D1. Weight loss: Weigh patient and assess for weight loss. Someone who is frail may have unintentional weight loss of ≥ 10 pounds in the prior year.
- D2. Gait speed: Time a patient's walk for slowness. Someone who is frail has a decreased walking time as defined by a timed 15-foot walk test (5 meters). The time is adjusted for gender and standing height. Men with a height of <173 cm and women with a height <159 cm who walked 15 feet in >7 sec are considered frail; men >173 cm and women >159 cm who walked 15 feet in >6 sec are considered frail.
- D3. Weakness: Weakness is established when there is decreased grip strength measured by a dynamometer with the value adjusted for gender and body mass index (BMI). Men with a BMI <24 are considered frail if the grip strength (kg) is <29, for a BMI of 24.1-28, a man is frail if <30, for a BMI >28 a man is frail if <32. For women, a BMI of <23 is considered frail if the grip strength (kg) is <17, a BMI 23.1-26 is considered frail if <18, and a BMI >29 is considered frail if <21.
- D4. Physical Activity: Determine if the patient has a low physical activity level. This is established by a weighted score of kilocalories expended per week measured by the Minnesota Leisure Time Activity Questionnaire. The questionnaire asks about activities like daily living, sports and hobbies. Frailty is present when males use <383kcal/week, and females <270 kcal/week.

D5. Frailty Phenotype: Score will be calculated based on presence of each of these characteristics where presence of 1-2 criteria are categorized as prefail, and >=3 criteria categorized as frail.

NOTE: APPENDICES F-H ARE UPLOADED AS SEPARATE DOCUMENTS WITHIN THE IRB APPLICATION

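### Frailty is analysed only as the Fried phenotype, although grip strength in kg and walk time in seconds are already recorded; in about 30 patients this discards information that could be kept at almost no cost

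*Combined protocol and SAP*

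**What the plan says.** Objective 2.3.7 reads "Assess the presence of frailty phenotype", and the endpoint in 2.5.3 reads "Presence of frailty phenotype using Fried's definition [50] will be evaluated". The matching hypothesis in 2.4.3 is "The frailty phenotype may be improved", with no size attached.

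Appendix E defines the phenotype in two steps. First, each component is cut at a threshold. For grip, one of the sex and BMI rules is "Men with a BMI <24 are considered frail if the grip strength (kg) is <29"; the walk is cut at more than 6 or more than 7 seconds, depending on sex and height. Second, under D5, the criteria are counted and the count is classed: "presence of 1-2 criteria are categorized as prefail, and >=3 criteria categorized as frail".

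The underlying values are collected. Section 5.1.16 says of grip "Three assessments for each hand will be completed and recorded", and of the walk "A timed walk-test from first foot fall to last foot fall over 15 feet will be performed twice per assessment". Sections 5.3.2, 5.4 and 5.6 place both tests at day 1 of cycles 1, 3 and 5 and at the End-of-Study visit. No endpoint in 2.5.2 or 2.5.3 uses kg or seconds.

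The regression steps in 9.2, including random effects for repeated measures, are set out for the secondary endpoints. Frailty is exploratory, so no test or model is named for it.

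**The concern.** The design has a single arm and 30 evaluable patients, so change within patients is the only evidence on frailty. Cutting a measurement at a threshold removes all movement that does not cross it, and counting and classing the criteria removes more. A patient whose grip rises by several kilograms but stays on one side of the cut contributes nothing to the endpoint.

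At stake is a modest but avoidable loss. The trial may report no change in frailty when the recorded strength and gait data would have shown one, or would have given a usable estimate with an interval. If the raw values are looked at only afterwards, someone must choose among six grip readings and two walk times per visit with no rule fixed beforehand.

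**Working it through.** The plan states no power, effect size or expected prevalence for frailty, so there is no figure to reproduce.

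**Inputs from the documents.** n = 30 evaluable (Study Summary); single arm; two-sided 0.05 (9.2, used here only as a yardstick); measures and visits as described above.

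**Assumptions, not in the documents.** Baseline proportion below a cut 20% to 50%; before/after correlation r of 0.6 to 0.8; change of 0.5 SD of the paired differences; normal measurements.

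**Step 1: a bound that needs no effect size.** In an exact McNemar test only patients who change class count. With b improving and none worsening, p = 2 x 0.5^b.
- b = 5: p = 0.0625
- b = 6: p = 0.031
- 7 improving and 1 worsening: p = 0.070
- 8 improving and 1 worsening: p = 0.039

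With five or fewer frail patients at baseline, significance on the yes/no scale is impossible. With six or seven, at least six must revert and nobody may become frail.

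**Step 2: one measure, continuous or cut.** For the paired t-test the noncentrality is 0.5 x sqrt(30) = 2.74 on 29 degrees of freedom, which gives power 0.75. For the cut version, 0.5 SD of the differences equals 0.5 x sqrt(2(1 - r)) SD of the measure: 0.447 at r = 0.6, 0.387 at 0.7 and 0.316 at 0.8. The bivariate normal then gives the probabilities of crossing the cut each way, and the exact McNemar power follows:

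| Below cut at baseline | r = 0.6 | r = 0.7 | r = 0.8 |
|---|---|---|---|
| 20% | 0.10 | 0.08 | 0.05 |
| 30% | 0.18 | 0.15 | 0.10 |
| 50% | 0.27 | 0.22 | 0.16 |

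If the change is expressed in SDs of the measure itself, the contrast remains. For 0.3 SD, power is 0.43 to 0.71 continuous and 0.04 to 0.14 cut. For 0.5 SD it is 0.84 to 0.99 continuous and 0.12 to 0.42 cut.

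**Step 3: the five-criterion phenotype.** Step 2 concerns one measure, and the endpoint is a composite. Simulated power at n = 30 for shifts of 0.3 to 0.5 SD:
- only grip and walk improve: yes/no 0.02 to 0.13, three classes 0.03 to 0.16
- four criteria improve together: yes/no 0.06 to 0.60, three classes 0.13 to 0.70

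A direct calculation on frail/not frail, with half of the frail reverting and 5% of the others becoming frail, gives 0.03, 0.14, 0.34 and 0.58 at 20%, 30%, 40% and 50% baseline frailty. The best case tried (50% frail, half reverting, none worsening) gives 0.80. If only 30% of the frail revert, power is at most 0.29.

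**Step 4: attrition.** With 20 patients at both time points, the raw measure has power 0.30 to 0.92. The phenotype has at most 0.29 (yes/no) or 0.40 (three classes).

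**Side observations on Appendix E.** The weight-loss criterion looks back one year, so loss before entry may still count during the 24 weeks. D3 gives no grip cut-off for women with BMI above 26 up to 29, and D1 to D5 give no scoring rule for exhaustion. Raw grip and walk time are not affected by these points.

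**The case against.** The strongest reply is that this criticises a test that the plan does not contain. Frailty is exploratory, 9.2 confines its modelling to secondary endpoints, and no power is claimed. That is correct, so the point is about information lost and not about an error.

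A reader might go further and infer that the planned outcome can hardly show improvement at all. The documents do not support that, for four reasons.
- The 5% to 27% describes one dichotomised measure, not a composite of five criteria. When several criteria improve together the phenotype does better (step 3). The criterion count that D5 calculates before classing does better still: simulated power with four items improving was 0.54 to 0.82 in one set of runs and 0.72 to 0.98 in another, again on assumed inputs.
- Only on the yes/no scale is improvement confined to patients who start frail. With the D5 classes, a prefrail patient can move to no criteria.
- Change on the non-frail side of a cut is not all hidden. A decline that crosses the cut is what the criterion records. With 20% to 30% below the cut and a decline of 0.5 SD of the paired differences, about 4 to 7 of 30 patients would newly cross it.
- It cannot be assumed that few patients will be frail at entry. Criterion 3.1.3 (ECOG 0-1 or Karnofsky above 60%) points that way, but 3.1.5 requires cachexia, so many may already meet or approach the weight-loss criterion.

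Physical activity is also measured on finer scales, since the wearable data are a secondary endpoint. That limits the loss but does not replace strength and gait. Finally, the raw values could be analysed later without any change to the plan. They could, but naming them and the rule for combining readings beforehand removes the choice after the data are seen.

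**Conclusion.** The point holds as an optional improvement. The plan records grip strength and walk time on continuous scales and defines an endpoint only from their thresholded form. Without any effect-size assumption, five or fewer frail patients at baseline rule out a significant yes/no improvement. With an assumed change of 0.5 SD of the paired differences in one measure, dichotomising lowers power from about 75% to about 5% to 27%. In all the single-measure scenarios calculated, the continuous measure did better than its own cut version.

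The gap is smaller, and of uncertain size, for the full phenotype or the criterion count if several criteria improve together. Baseline frailty, effect size and correlation are all assumptions. On either scale, a single arm shows change over time and cannot attribute it to the enzymes.

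**What to change.** In 2.5.3, keep the Fried class and the criterion count as the summary of the phenotype, and add two exploratory outcomes: change from C1D1 in grip strength (kg) and change from C1D1 in 15-foot walk time (seconds). State one rule for combining readings, for example the maximum reading of the stronger hand for grip and the mean of the two trials for the walk.

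In 9.2, extend the repeated-measures model planned for secondary endpoints to these two outcomes on their continuous scale. Report estimates with 95% confidence intervals at C3D1, C5D1 and End-of-Study. State that the End-of-Study value is taken about 30 days after the last dose of study drug. Label both outcomes as exploratory, without multiplicity control, and as before/after change and not an enzyme effect.

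The cost is a few sentences in two sections and two more exploratory outcomes to report. No new assessments, visits, patients or staff are needed.

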3.0 PATIENT ELIGIBILITY

Subjects must meet all of the inclusion and exclusion criteria to be registered to the study. Study treatment may not begin until a subject is registered.

3.1 Inclusion Criteria

- **3.1.1** Borderline resectable, locally advanced, and advanced pancreatic cancer patients (can include new or recurrent diagnosis) referred to SOCCI-CSMC
- **3.1.2** Age ≥ 18 years.
- 3.1.3 ECOG performance status 0-1 or Karnofsky PS >60% (Appendix A)
- **3.1.4** Clinical diagnosis of exocrine pancreatic insufficiency
- 3.1.5 Cachexia defined as ≥5% weight loss in the presence of chronic illness, within any 6-month period prior to screening OR as documented by the medical physician based on standard diagnosis of cachexia
- **3.1.6** Life expectancy of greater than 3 months, in the opinion of the investigator.
- **3.1.7** Patients must have normal organ and marrow function as defined below:

Absolute Neutrophil Count (ANC)	≥500/mcL
Platelets	≥50,000/mcL
Total bilirubin	≤ 5X upper limit of normal (ULN)
AST(SGOT)/ALT(SGPT)	≤ 5 X ULN
Creatinine OR creatinine clearance	≤ 3 times the upper limit of normal OR ≥ 30 mL/min/1.73 m² for patients with creatinine levels above normal.

Note: Patients with biliary stents are eligible provided that all other inclusion criteria are met.

- **3.1.8** Woman of child-bearing potential (WOCBP) and men must agree to use adequate contraception (hormonal or barrier method of birth control; abstinence) from the time of signing the informed consent form, for the duration of study participation, and for at least 30 days after discontinuing from study treatment.
- **3.1.9** Ability to understand and the willingness to sign a written informed consent document

3.2 Exclusion Criteria

- **3.2.1** Uncontrolled intercurrent illness including, but not limited to, ongoing or active infection, symptomatic congestive heart failure, unstable angina pectoris, cardiac arrhythmia, or psychiatric illness/social situations that would limit compliance with study requirements.
- 3.2.2 Women who are pregnant or are breastfeeding
- **3.2.3** Dementia or altered mental status that would prohibit the understanding or rendering of informed consent
- **3.2.4** Unable to swallow intact capsules
- **3.2.5** Fibrosing colonopathy: Patients with history of fibrosing colonopathy have been reported to experience advancement to colonic strictures with doses of lipase>6000 units/kg/meal over prolonged periods of time.
- **3.2.6** History of chronic illness associated with malabsorption or nutrient deficiency including but not limited to chronic pancreatitis, cystic fibrosis, celiac disease, Crohn's disease, pernicious anemia and/or prior intestinal resection.
- **3.2.7** Pregnancy, breastfeeding, or of childbearing potential and not willing to use methods of birth control during the study
- **3.2.8** Active drug abuse or intoxication with any substance including alcohol (blood alcohol content >0.08%, legal driving limit)
- **3.2.9** Known allergy to any of the active ingredients in pancreatic enzyme supplementation
- **3.2.10** Concurrent use of pancreatic enzyme supplementation or over the counter supplements which contain lipase, protease, and amylase as active ingredients

4.0 TREATMENT PLAN

4.1 Treatment Dosage and Administration

4.1.1 Agent Administration

Treatment will be administered on an outpatient basis. The investigational treatment cycle is every 4 weeks. Patients removed from study for unacceptable adverse events will be followed until resolution or stabilization of the adverse event.

Subjects meeting enrollment criteria will be given Pancreaze (84,000 lipase units per main meal and 42,000 lipase units per snack). Subjects will undergo treatment with pancreatic enzymes indefinitely as per standard therapy for patients with EPI. If symptoms and signs of steatorrhea persist, the dosage may be increased by the healthcare professional.

If doses are to exceed 2,500 lipase units/kg of body weight per meal, further investigation is warranted. Doses greater than 2,500 lipase units/kg of body weight per meal (or greater than 10,000 lipase units/kg of body weight per day) should be used with caution and only if they are documented to be effective by 3-day fecal fat measures that indicate a significantly improved coefficient of fat absorption. Doses greater than 6,000 lipase units/kg of body weight per meal have been associated with colonic stricture, indicative of fibrosing colonopathy, in children less than 12 years of age. Patients currently receiving higher doses than 6,000 lipase units/kg of body weight per meal should be examined and the dosage either immediately decreased or titrated downward to a lower range.

Subjects will be instructed to take 84,000 units (4 capsules) per main meal and 42,000 units (2 capsules) per snack. Should dose reductions be required per treating investigator, the guidelines in Section 4.1.3 will be followed.

4.1.2 Drug Interactions

No drug interactions have been identified. No formal interaction studies have been conducted.

Patients taking fat-soluble vitamin supplements will be advised to discontinue use while on this trial as it is likely to interfere with the proposed study assessments.

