4.2 Concomitant Medications

Concurrent use of other pancreatic enzyme supplementation, fat-soluble vitamin supplements, or over the counter supplements which contain lipase, protease, and amylase as active ingredients is not permitted.

Only conmeds that are used to treat an adverse event deemed at least possibly related to Pancreaze need to be recorded in the REDCap database.

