5.1.10 Review previous and concomitant medications

5.1.11 Blood collection for general health assessment

CBC with differential, CMP, Phosphorus, Magnesium. Phosphorus and Magnesium will be assessed at C1D1 only.

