5.2 Screening/Baseline Procedures

Assessments performed exclusively to determine eligibility for this study will be done only after obtaining informed consent. Assessments performed for clinical indications (not exclusively to determine study eligibility) may be used for baseline values even if the studies were done before informed consent was obtained.

All screening procedures used for eligibility verification must be performed within 4 weeks of Day 1 unless otherwise stated. Baseline procedures not required for eligibility verification can occur on Cycle 1, Day 1 of treatment (See section 5.3).

The screening and baseline procedures include:

- Informed consent
- Eligibility review, including:
 - Pregnancy test
- Demographics
- Medical/Surgical history
- Complete physical exam
- Standard of care CT imaging
- Height, weight, vital signs
- Performance status (ECOG or Karnofsky)
- AE (baseline symptom) assessment

- Concomitant medications review
- Labs: CBC/diff, CMP
- Blood draw for fat soluble vitamin levels
- Fecal elastase
 - Note: for maximum flexibility for the patients, the fecal elastase stool sample may be collected during screening or until C1D1 (+ 7 days).
 Patients will be encouraged to provide the fecal elastase stool sample prior to starting treatment, if possible.

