6.0 ADVERSE EVENTS

6.1 Adverse Event Monitoring

The investigator or designee is responsible for ensuring that adverse events (both serious and non-serious) observed by the clinical team or reported by the subject which occur after the subject has initiated treatment and until the 30-day end-of-study visit, are fully recorded in the subject's medical records. Source documentation must be available to support all adverse events.

A laboratory test abnormality considered clinically relevant (e.g., causing the subject to withdraw from the study, requiring treatment or causing apparent clinical manifestations, result in a delay or dose modification of study treatment, or judged relevant by the investigator), should be reported as an adverse event.

The investigator or sub-investigator (treating physician if applicable) will provide the following for all adverse events (both serious and non-serious):

- Event term (as per CTCAE) Descriptions and grading scales found in the NCI Common Terminology Criteria for Adverse Events (CTCAE) version 5 will be utilized for AE reporting.
- Description of the event
- Date of onset and resolution
- Expectedness of the toxicity
- Grade of toxicity
- Attribution of relatedness to the investigational agent- (this must be assigned by an Investigator, sub-investigator, or treating physician)

- Action taken as a result of the event, including but not limited to; no changes, dose interrupted, reduced, discontinued, etc. or action taken with regard to the event. i.e. no action, received conmed or other intervention, etc.
- Outcome of event

All patients experiencing an adverse event, regardless of its relationship to study drug, will be monitored until:

- the adverse event resolves or the symptoms or signs that constitute the adverse event return to baseline
- any abnormal laboratory values have returned to baseline
- there is a satisfactory explanation other than the study drug for the changes observed, or
- death

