6.2 Protocol-specific Adverse Event Monitoring Guidelines

Since this supplement is FDA approved as part of standard of care in the patient population under study, only AEs of interest, as outlined below, will be collected and recorded in the EDC:

- Any event deemed serious and expected OR unexpected, regardless of cause.

 AND
- AEs of interest included below:

Expected toxicities to Pancreaze
Abdominal pain
Abdominal pain upper
Flatulence
Diarrhea
Abnormal feces
Fatigue

Note; All expected toxicities from chemotherapy can be found in the FDA approved Package Insert.

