9.2 Data Analysis Plan

The primary hypothesis to be tested is whether is the percentage of patients who complete the pancreatic enzyme replacement therapy at 8 weeks is at least 50% for each of the three cancer stage subgroups: borderline resectable, locally advanced and advanced pancreatic cancer. A 95% confidence interval [1] for the proportion of treatment completeness will be calculated for each cancer stage. The statistical analysis will be performed in three steps for all secondary endpoints: 1) Descriptive analysis: Measures of central tendency (mean, median and mode), measures of variability (standard deviation, range and quantiles). Standard distribution plots such as profiles-plots for repeated measures and box-plots will be constructed to examine the distribution of the data. 2) Univariable Analysis and 3) Multivariable analysis: The linear regression model will be applied to explain the secondary endpoints as a function of the patient's baseline variables. Assumptions of the linear regression model will be examined. If the assumptions are not met. Generalized Additive models for Location, Scale and Shape (GAMLSS) which provide a general framework for extending a standard linear model will be applied [2]. The goodness of fit for each model will be accessed through a residual analysis using Worm-plots [51] and variable selection will be performed as outlined by Harrell [4]. Random effects will be added to describe the repeated measures. In addition, overall survival curve will be estimated using the Kaplan-Meier method with 95% confidence interval. All tests of hypotheses will be two-sided and a significance level of 0.05 and calculations will be performed using R, version 3.2.3 [5].

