10.6.3 Other Protocol Deviations

Logistical deviations from the protocol (e.g., minor changes to the study schedule for an individual subject) do not require prior IRB approval unless the deviation has the potential to affect the subject's safety or study integrity. Such planned deviations that do meet this definition and do not affect the subject's safety or study integrity should be noted in the

subject's research record or deviation log as described in the SOCCI CCTO's Standard Operating Procedure 12: Deviation and Noncompliance Reporting.

Unintentional deviations from the protocol that might affect subject safety or study integrity should be reported to the IRB within 10 days from when the investigator becomes aware that such a deviation has occurred, as outlined in the SOCCI CCTO's Standard Operating Procedure 12: Deviation and Noncompliance Reporting. In this case, a Protocol Deviation report must be submitted in CS-IRB, per IRB policy, Reporting Possible Unanticipated Problems Involving Risks to Subject or Others (UPIRSO) Policy: Institutional Review Board/Research Compliance and Quality Improvement. All submissions should include a description of the plan to avoid similar deviations or exceptions in the future.

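### Fat-soluble vitamin supplements are stopped with no washout before the baseline draw and no duty to enter their use in REDCap, so the before-after vitamin change may be biased and its separation from supplement changes is not assured

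*Combined protocol and SAP*

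**What the plan says.** Section 4.1.2 of the protocol states that "Patients taking fat-soluble vitamin supplements will be advised to discontinue use while on this trial", and gives as the reason that supplements would probably disturb the study's measurements. Section 4.2 goes further and does not permit concurrent use. Prior use does not bar enrolment: exclusion 3.2.10 covers products containing pancreatic enzymes, not vitamins.

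Section 4.2 also sets the recording rule: "Only conmeds that are used to treat an adverse event deemed at least possibly related to Pancreaze need to be recorded" in REDCap. A vitamin supplement taken before the trial, the date it was stopped and a later restart would not generally meet that condition.

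Vitamins A, D, E and K are a secondary endpoint (2.5.2), measured at baseline and at End-of-Study, with improvement as the hypothesis (2.4.2). The baseline draw is listed among the screening and baseline procedures in section 5.2, which adds that "Baseline procedures not required for eligibility verification can occur on Cycle 1, Day 1 of treatment". The second draw falls 30 days after the last dose, plus or minus 7 days (5.4). Section 9.2 uses regression to "explain the secondary endpoints as a function of the patient's baseline variables", and does not name supplement use among those variables.

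**The concern.** The protocol identifies supplements as a threat to its own measurements and then directs a change in their use around the two draws that define the endpoint. With one arm, no control group cancels the effect of that change.

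The timing is open. The advice to stop carries no date, no washout is set, and baseline may be drawn at screening or on Cycle 1 Day 1. One user's baseline may thus be a supplemented level and another's not, and no required field shows which. By comparison, section 4.1.3 requires enzyme dose modifications to be recorded with their dates.

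At stake is the reading of one secondary result. A real gain from enzymes could be hidden by stopping supplements, or a restart could pass for a gain. The feasibility conclusion rests on lipase units taken in the first 8 weeks and does not depend on vitamin levels.

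**Working it through.** The plan gives no vitamin data, share of users or precision figure for this endpoint, so there is no stated number to reproduce. The text comparison carries the point. The arithmetic only shows what size is plausible, and every input except the 30 evaluable patients is an assumption.

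**Step 1: what must be in the database.**

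| Item needed | Required REDCap entry? | Other possible source |
|---|---|---|
| Supplement use at screening | No explicit duty (4.2) | Medication review (5.1.10, 5.2) |
| Stop date relative to baseline draw | No explicit duty | Medication review, if dates are noted |
| Restart before the End-of-Study draw | No explicit duty | Review each cycle and at End-of-Study; deviation log (10.6.3) |
| Vitamin levels at both draws | Collected (5.1.13, 5.6) | – |

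**Step 2: direction.** If a user's baseline is a supplemented level and the supplement stays stopped, the change is pushed down. If baseline was drawn off supplements and they restart before the second draw, it is pushed up. If baseline was supplemented and supplements restart, the two tend to offset.

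**Step 3: shift in the mean change.** Let p be the share of users with a supplemented baseline and d their fall in SD units. Shift = −p × d.
- Low: 0.10 × 0.25 = 0.025 SD down
- Middle: 0.25 × 0.50 = 0.125 SD down
- High: 0.40 × 0.75 = 0.30 SD down

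For restarts, the shift is the share restarting times their rise, with the opposite sign. For vitamin K, PIVKA-II and prothrombin time worsen upward, so the sign is reversed.

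**Step 4: precision of the mean change.** With correlation ρ between the two draws and n complete pairs, SE = √(2(1 − ρ)/n) in SD units.

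| Pairs | ρ = 0.3 | ρ = 0.5 | ρ = 0.7 |
|---|---|---|---|
| 30 | 0.216 | 0.183 | 0.141 |
| 27 (non-users if 10% are users) | 0.228 | 0.192 | 0.149 |
| 18 (non-users if 40% are users) | 0.279 | 0.236 | 0.183 |
| 15 | 0.306 | 0.258 | 0.200 |

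With 30 pairs the middle shift is below one standard error and the high shift is above it. Restricting to non-users costs little precision.

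**Step 5: user versus non-user contrast.** SE = √(2(1 − ρ)(1/n₁ + 1/n₂)), for ρ from 0.7 to 0.3.
- 12 versus 18: 0.29 to 0.44 SD
- 3 versus 27: 0.47 to 0.72 SD
- 4 versus 11 (15 pairs): 0.45 to 0.69 SD

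This contrast is too imprecise to measure the effect of withdrawal.

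**Step 6: crossing a deficiency limit.** Assume bivariate normal levels, 20% to 40% deficient at baseline and ρ from 0.3 to 0.7. With no shift at all, 9% to 19% cross into deficiency and the same share cross out. A 0.5 SD fall in users only (10% to 40% of the cohort) adds 1.2 to 5.2 percentage points crossing in, or 0.4 to 1.6 patients in 30. A shift table must therefore show both directions.

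**The case against.** The strongest reply is that section 4.2 sets a minimum and does not forbid other entries, and that the case report forms are not in the documents. Section 5.1.10 ("Review previous and concomitant medications") names earlier medications separately, so prior use found at screening may be captured anyway. Reviews recur on day 1 of each cycle and at End-of-Study. A restart while supplements are prohibited would be a deviation, for which section 10.6.3 points to the "subject's research record or deviation log as described". In a single-centre trial of at most 40 patients, chart abstraction is feasible, and the unspecified baseline variables in section 9.2 could include prior use.

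Most of this stands. A reader might infer that the data cannot separate the vitamin change from supplement withdrawal. The documents do not support that. They show only that no explicit duty assures it.

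Two other strong readings also fail.
- A reader might infer that new vitamin deficiency would go unseen, because section 6.2 says "only AEs of interest, as outlined below, will be collected and recorded in the EDC" and its list does not name deficiency. But the two measured levels already allow new laboratory-defined deficiency to be counted, and section 6.1 makes a clinically relevant laboratory abnormality, for example one "requiring treatment or causing apparent clinical manifestations", an adverse event in the medical record.
- A reader might infer that the bias is always downward. Step 2 shows that a restart can reverse it.

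It is also fair to say that the effect may be small, and that eligibility asks only for a life expectancy above 3 months, so fewer than 30 pairs may reach the second draw. Neither removes the gap: the size depends on the share and timing of users, which the required fields do not record.

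**Conclusion.** The point holds and is minor. The protocol itself creates and names a confounder of a secondary endpoint, sets no washout, and then omits that confounder from required data entry. The before-after vitamin change may be biased in either direction, and separating that bias is possible from source records but not assured.

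The size is unknown. Under the assumed ranges the mean moves down 0.025 to 0.30 SD, with a middle case of 0.125 SD against a standard error of 0.14 to 0.22 SD. These figures assume 30 complete pairs, supplemented baselines in all users, and no restarts. Confidence is medium, because the case report forms may already hold more than the text requires.

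**What to change.** **Section 4.2.** As an exception to the recording rule, enter in REDCap at the existing medication reviews:
- which of vitamins A, D, E and K each patient was taking at screening, with product and dose if known;
- the stop date relative to the baseline draw;
- any restart date up to the End-of-Study draw.

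Use must be held per vitamin. A single yes/no item would count a patient taking only vitamin D as a user for A, E and K.

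**Section 9.2.** Report each vitamin's change overall and by prior use of that vitamin, with 95% confidence intervals. Present the non-user estimate as the one free of withdrawal. Label the results descriptive: there is no control arm, and the second draw is about 30 days after the last dose, when some patients may be on standard-of-care enzymes (5.3.3). A descriptive two-way shift table of paired levels may be added, stating how many patients lack a second sample. Section 6.2 needs no change.

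**Cost.** A few more data entries, with no new visit or blood draw. The intervals will be wide, especially among users.
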